11.2.2 Analysis of the Primary Endpoint(s)

Feasibility will be analyzed using attendance and retention rates. For the proposed study to be considered feasible, we will need to uphold all the following criteria: 70% of participants attend all intervention sessions and 85% of participants are retained throughout the study (from pre-intervention to post-intervention assessment). These proportions are based on previously successful CBSM trials in other populations.

We will also perform descriptive analyses to better understand the feasibility of our future R01 trial, including:

- 1) Personnel time: This will include personnel time that is devoted to assessing eligibility, managing contacts, and recruiting, conducting the intervention, and administrative time.
- 2) Space: We will collect information on any space used that is needed to conduct the intervention, including administrative space.
- 3) Supplies: We will collect information on all supplies that are needed and any costs associated with maintaining the SmartManage website.

Acceptability will be analyzed using the proportion of the number of participants who agree to participate in the intervention. We will evaluate the acceptability of the intervention two ways:

1) via the proportion of eligible SMM who agree to participate vs. decline and 2) via the exit survey that will measure acceptability of the intervention.

We will explore whether feasibility and acceptability differ by sociodemographic, medical, and psychosocial factors via Fisher's exact tests. These analyses will be primarily descriptive and will provide the basis for future randomized trials to formally evaluate the efficacy of the culturally-tailored web-based SmartManage intervention among dually-diagnosed Latino SMM.

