1 PROTOCOL SUMMARY

Title	A Culturally-Tailored Web-Based Cognitive Behavioral Stress Management for Latino Sexual Minority Men living with HIV and Cancer	
Background	
HIV infection is associated with increased risk for several types of cancer, including but not limited to Kaposi's sarcoma, non-Hodgkin lymphoma, and anal cancer. With an increasing aging HIV-positive (HIV+) population, which includes large proportions of ethnic and sexual minority individuals, there has also been a substantial increase in the proportion of these individuals who develop and survive cancer.
 
Living with a dual-diagnosis of HIV and cancer can increase distress, as well as affect multiple aspects of health-related quality of life (HRQoL). Moreover, among dually-diagnosed individuals, those who are ethnic and sexual minorities may experience more substantial cancer survivorship disparities. For example, prior research indicated sexual minority cancer survivors experience higher distress and poorer self-rated health than their heterosexual counterparts.
 
Our prior research demonstrated the efficacy of a cognitive behavioral stress management (CBSM) intervention in improving psychosocial and health outcomes for individuals living with HIV or cancer. Thus, we propose a single-arm feasibility trial of a culturally-tailored web-based CBSM intervention for dually-diagnosed (HIV/cancer) Latino sexual minority men (SMM).
	
Objectives/Endpoints	Objectives	Endpoints
	
Primary: To examine the feasibility and acceptability of the culturally-tailored web-based SmartManage intervention among dually-diagnosed Latino SMM.
 
Secondary: To evaluate the preliminary efficacy of the culturally-tailored web-based SmartManage intervention among dually-diagnosed Latino SMM.
	
Feasibility will be examined via retention (> 85%) and attendance (> 70%) rates. We will evaluate acceptability via quantitative assessment as well as open-ended feedback.
 
Intended effects will be evaluated via examining pre-post changes in health-related quality of life, general stress, and disease/dual-diagnosis related distress using the following measures: Functional Assessment of Cancer Therapy Scale-General, Medical Outcomes Study HIV Survey, Perceived Stress Scale, and Impact of Event Scale.

Study Design	Single-arm feasibility trial	
Number of Patients/ Target Study Population	30 Latino sexual minority men living with both HIV and cancer	

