3.1 Endpoints

Feasibility will be examined via retention (> 85%) and attendance (> 70%) rates. Acceptability will be evaluated via quantitative assessment as well as open-ended feedback. These assessments will measure standard dimensions of acceptability including relative advantage, compatibility, and complexity.

Intended effects will be evaluated via examining between-group pre-post changes in health- related quality of life, general stress, and disease/dual-diagnosis related distress.

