5.2 Recruitment and Retention Methods

For this 1-year pilot, we plan to recruit 30 Latino HIV+ cancer survivors who are sexual minority men. By working with a variety of UM and UM-affiliated groups, including Sylvester Comprehensive Cancer Center as well as our external partners we hope to enroll HIV+ cancer survivors of diverse backgrounds, in terms of age, education, and socioeconomic status. We acknowledge that recruiting this many patients from such a unique population and within the proposed timeframe may present several challenges. However, study staff will capitalize on their working relationships with University of Miami Medicine affiliates and their connections to community partners.

Screening and Recruitment: Participants for this pilot will be recruited remotely (online or by phone). For this study, staff will utilize these primary avenues for participant recruitment: 1) the University of Miami Medicine system and its University of Miami affiliates (e.g., Sylvester Comprehensive Cancer Center, consent to contact lists from other University of Miami investigators), 2) online advertising via social media, and 3) collaboration with external partnering community-based organizations.

University of Miami Medicine and its UM affiliates (UHealth Clinics, UM Consent to Contact Database, or Other UM Investigators' Consent to Contact Lists)

A partial HIPAA waiver is requested for screening and recruitment purposes (See section 12.1.3 for HIPPA Waiver). Such a waiver is appropriate for the following reasons:

- a) This study is of no more than minimal risk to prospective patient/participants, as their participation simply involves undergoing a psychosocial intervention and providing questionnaires and does not utilize drugs, medical devices, or medical procedures of any kind.
- b) Personal identifiers obtained via the report will be used to determine patients' eligibility for enrollment only and will be destroyed as soon as possible after the determination of eligibility is made.
- c) All other personal health information (PHI) collected from patients will be obtained by self-report only. For the purpose of this pilot, study staff is *not* requesting access to enter patients' electronic medical records beyond the pre-screening.

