11.1 Sample Size Determination

We expect that, within this subgroup of HIV+ sexual minority men, rates of prevalence of cancer will likely be greater or equal to 30% (i.e. the rate of prevalence observed in the general older male population). This estimate, along with consultations with our co-investigators and community partners has informed our recruitment goals. Based on our institution accrual capacity, we are able to enroll 30 subjects in the study. In accordance with Leon et al. 2011,²⁹ we assert that the main goal of our pilot study is to examine the feasibility and acceptability of a culturally-tailored SmartManage intervention and based our sample size on the number of participants that could feasibly be recruited within our time frame. Thirty participants will be assessed for retention and attendance rates. As detailed here, 30 participants provide reasonable precision for estimating the above rates. Table 1 illustrates study precision for estimating the true attendance rate. If we observe 21 participants among 30 who attend all intervention sessions, the estimated attendance rate will be 70% and the corresponding 95% confidence interval will be 50.6% to 85.3%. If the number of participants who attend all intervention sessions is 27, then the estimated attendance rate will be 90% with a corresponding 95% confidence interval of 73.5% and 97.9%. Furthermore, with 30 participants, a one-sided binomial test with 5% significance will have power >80% to detect improvement to 18.6% attendance relative to a null rate of 70%.

Table 1. Possible study findings for attendance rate with 30 subjects

Number (%) of attended subjects	95% CI*
21 (70%)	50.6% - 85.3%
24 (80%)	61.4% - 92.3%
27 (90%)	73.5% - 97.9%

* CI: confidence interval, binomial method.

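### Does the missing inequality sign in section 11.2.2 leave the feasibility verdict undecided at 21 of 30?

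*Combined protocol and SAP*

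**What the plan says.** The cut-offs appear in three places. The endpoints row of the Protocol Summary and section 3.1 both say "Feasibility will be examined via retention (> 85%) and attendance (> 70%) rates". Neither says there what counts as attendance.

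Section 11.2.2 turns these rates into a decision: "For the proposed study to be considered feasible, we will need to uphold all the following criteria", and the criteria are that "70% of participants attend all intervention sessions and 85% of participants are retained throughout the study". The unit is given here (participants who attend every session), but no inequality sign is.

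Section 11.1 fixes the planned denominator: "Thirty participants will be assessed for retention and attendance rates". It uses the same unit as 11.2.2, and the first row of its Table 1 is 21 of 30, or 70%, with a 95% interval of 50.6% to 85.3%. It also mentions a test against a null rate of 70%, for which "a one-sided binomial test with 5% significance will have power >80% to detect improvement".

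**The concern.** A pass/fail rule should say what happens on its boundary, and here the boundary can be reached: 70% of 30 is a whole number, and Table 1 lists it as a possible finding. Under the sign in the Summary and 3.1, 21 of 30 fails. Under a common reading of a bare percentage in 11.2.2, it passes. Both criteria must be met and feasibility belongs to the primary objective, so if retention were also met, one participant could decide the feasibility conclusion. If attendance data already exist, an unstated sign might also look like room to choose the verdict afterwards.

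**Working it through.** **Inputs.** N = 30 and the Table 1 rows (11.1); attendance > 70% and retention > 85% (Summary and 3.1); 70% and 85% without a sign (11.2.2). The true attendance rate *p* is not given, so a range is shown.

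**Reproducing Table 1.** Exact (Clopper-Pearson) limits for *x* of *n* are the 2.5% quantile of Beta(*x*, *n* − *x* + 1) and the 97.5% quantile of Beta(*x* + 1, *n* − *x*). For *n* = 30 they are:
- *x* = 21: 50.6% to 85.3%
- *x* = 24: 61.4% to 92.3%
- *x* = 27: 73.5% to 97.9%

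All three rows agree with the plan.

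**Counts at N = 30.**
- Attendance: 0.70 × 30 = 21. At least 70% needs 21; more than 70% needs 22 (22/30 = 73.3%).
- Retention: 0.85 × 30 = 25.5. Both readings need 26 (26/30 = 86.7%).

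Only the attendance count of 21 separates the readings.

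**Counts if accrual falls short.** Section 5.2 concedes that "recruiting this many patients from such a unique population and within the proposed timeframe may present several challenges". The minimum counts are the same on both readings for N = 26 to 29:

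| N | 0.70 × N | Attendance | 0.85 × N | Retention |
|---|---|---|---|---|
| 26 | 18.2 | 19 | 22.1 | 23 |
| 27 | 18.9 | 19 | 22.95 | 23 |
| 28 | 19.6 | 20 | 23.8 | 24 |
| 29 | 20.3 | 21 | 24.65 | 25 |

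**Chance of landing on 21 of 30.** With *X* ~ Binomial(30, *p*), P(*X* = 21) = C(30, 21) × *p*^21 × (1 − *p*)^9. At *p* = 0.70 this is 14,307,150 × 0.70^21 × 0.30^9 = 0.157.

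| True rate | P(X ≥ 21) | P(X ≥ 22) | P(X = 21) |
|---|---|---|---|
| 0.70 | 0.589 | 0.432 | 0.157 |
| 0.75 | 0.803 | 0.674 | 0.130 |
| 0.80 | 0.939 | 0.871 | 0.068 |
| 0.90 | 0.9995 | 0.998 | 0.002 |

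P(*X* = 21) is largest at *p* = 21/30 = 0.70, so 0.157 is its maximum over all true rates. Each entry in the last column is an upper bound on the chance that the sign changes the overall verdict, because retention must also reach 26 of 30.

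**Reading the sections together.** The Summary and 3.1 give the sign but not the unit; 11.2.2 gives the unit but not the sign. Neither contradicts the other on what it leaves out. Combined, they give more than 70% of participants attending all sessions and more than 85% retained: at least 22 and at least 26 of 30.

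**The case for a change.** The strongest case for a change is that 11.2.2 alone states the decision rule, and it neither repeats the sign nor refers back to 3.1. An analyst working only from section 11 could pass 21 of 30 in good faith. Near a true rate of 70% that count occurs about one time in six, and inserting two words would settle the matter. Section 12.0.3 describes contacting people whose participation has ended as well as those still taking part, so attendance data may already exist; choosing the sign after seeing 21 would be choosing the verdict.

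It stands that 11.2.2 omits the sign and that 21 of 30 is attainable. The rest is weaker. Passing 21 of 30 requires an *at least* that no section contains, while the strict sign is printed twice, once in the endpoint definition itself. That printed sign also answers the worry about hindsight, since a later move to *at least 70%* would be a visible departure from 3.1. The missing unit in the Summary and 3.1 is readily supplied from section 11, and the missing sign in 11.2.2 deserves the same treatment. The test in 11.1 treats 70% as the value to improve on, which leans towards the strict reading but does not prove it, because it stands in the sample size section. An exact 5% test would need 26 of 30, since P(*X* ≥ 25) = 0.077 and P(*X* ≥ 26) = 0.030 at *p* = 0.70. Whether that test should bear on the verdict is a separate question that this point does not settle.

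**Conclusion.** No change is needed. Section 11.2.2 leaves out a sign that the Summary and 3.1 supply; it does not state a different one, and no stated rule gives a wrong result. Read as a whole, the plan requires at least 22 of 30 for attendance and at least 26 of 30 for retention.

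The omission could affect one count, at full accrual only, with probability at most 0.157 and much less if true attendance is well above 70%. Even then the evidence reported would hardly differ: the exact interval is 50.6% to 85.3% at 21 of 30 and 54.1% to 87.7% at 22 of 30, and the plan describes its analyses as mainly descriptive. Adding *more than* in 11.2.2 would be reasonable tidying if the protocol were being amended for another reason, but it would not alter the rule.

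This conclusion assumes that the denominator is the thirty participants named in 11.1 and that the rule is applied to observed proportions, as 11.2.2 is worded. The probabilities also assume that participants attend independently with a common rate.

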6 STUDY PROCEDURES

Study staff will follow guidelines from the CTSI on e-consenting using REDCap. After consent has been obtained, study staff will instruct the participant to complete the intake questionnaire.

Intake questionnaire:

- a) **Demographics and Disease Information:** Participants will complete: a demographic survey which will include factors such as age, race, education, employment status, income, nativity, years in the US, and relationship status. Participants will also complete a disease information form, which will collect medical history relevant to their cancer and HIV diagnoses. Finally, participants will complete ACTG HIV medication Adherence measure,¹⁹ and the Barriers to HIV Care survey.²⁰
- b) **Psychosocial Factors:** Participants will complete the Coping Self-Efficacy scale,²¹ Interpersonal Support Evaluation List (ISEL),²² the Bidimensional Acculturation Scale for Hispanics,²³ and the Computer Proficiency Questionnaire (CPQ).²⁴
- c) **Intervention Outcomes:** Participants will complete: the Perceived Stress Scale (General Stress),²⁵ the Impact of Event Scale (Disease/Dual-diagnosis-related Distress),²⁶ and The Functional Assessment of Cancer Therapy scale-General (FACT-G; HRQoL),²⁷ and Medical Outcomes Study HIV Survey (MOS-HIV; HRQoL).¹⁹
- d) **COVID-19 Questions:** Participants will complete the COVID-19 Impact of the Pandemic and HRQOL in Cancer Patients and Survivors measure.
- e) **Computer Proficiency:** Measured with the Computer Proficiency Questionnaire.

Once participants complete the intake questionnaire, they will be prompted to register on the culturally-tailored SmartManage intervention website. Study staff members who have previous experience and expertise in delivering CBSM interventions to Latino populations will conduct the study intervention interactive sessions. Following the intervention, participants will be prompted to complete their exit questionnaire in REDCap.

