11.2 Statistical Analyses

11.2.1 General Approach

All data will be inspected for quality assurance prior to analysis. Data screening will focus on: (a) Missing data: we will determine the amount, the pattern, and randomness; (b) Outliers: we will identify observations that appear to be very high or very low and decide how to proceed based on the presumed cause; and (c) Inconsistencies: we will identify inconsistencies within a single variable and between variables. Initially, we will perform an exploratory data analysis and calculate descriptive statistics.

Transformations of the data in order to meet statistical assumptions will be undertaken when indicated. Type-1 error will be set to 5% ($\alpha = .05$) for calculating confidence intervals and performing hypothesis testing and all tests will be two-sided. If needed,

alphas will be adjusted accordingly for multiple comparisons using Bonferroni correction. Standard statistical goodness-of-fit measures will be used assessing any of the model fittings. Missing values will be handled with appropriate statistical methods. Last observation carried forward (LOCF) and multiple imputation will be considered for missing values.

Demographic and disease characteristic variables will be summarized using descriptive statistics. Counts and percentages will be used to summarize the distribution of categorical variables. Median, range, mean, and standard deviation will be used for continuous variables. Categorical variables will be tested using Fisher's exact test. Continuous variables will be tested using Student's t-test and/or Mann-Whitney U test. For correlation coefficients, Pearson's correlation coefficients and Spearman's correlation coefficients will be estimated along with corresponding 95% confidence interval. All statistical analyses will be carried out using SAS or SPSS, all of which are available to investigators through the University of Miami.

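### Section 11.2.2 names only Fisher's exact tests for factors that include numeric scores, against 11.2.1, and psychosocial scores do not exist for men who decline

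*Combined protocol and SAP*

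**What the plan says.** Section 11.2.2 (Analysis of the Primary Endpoint(s)) gives one method for all three classes of factor: "We will explore whether feasibility and acceptability differ by sociodemographic, medical, and psychosocial factors via" Fisher's exact tests. It gives no cut points. It measures acceptability in two ways: the share of eligible men who agree rather than decline, and the exit survey. It describes these explorations as mainly descriptive and as groundwork for later randomized trials.

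Section 11.2.1 (General Approach) separates the methods by type of variable: "Categorical variables will be tested using Fisher's exact test", and "Continuous variables will be tested using Student's t-test and/or Mann-Whitney U test". It sets the type I error at 5% and says that "all tests will be two-sided".

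Section 6 (Study Procedures) fixes when the factors are measured: "After consent has been obtained, study staff will instruct the participant to complete the intake questionnaire". That questionnaire holds the demographic survey, the disease information form and the psychosocial scales. On the last of these it says "Participants will complete the Coping Self-Efficacy scale", together with the social support, acculturation and computer proficiency instruments.

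**The concern.** There are two separate difficulties.

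**Test and type of variable.** Fisher's exact test needs a contingency table. A multi-item scale score, age or years in the US enters one only after being cut into groups. Under 11.2.2 as written, the analyst would have to choose the cuts, possibly after seeing the data. The result can depend on that choice, and cutting discards information in a sample of 30.

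**Availability of the data.** One of the two acceptability measures compares men who agree with men who decline. The psychosocial scales are completed only after consent, so they are missing for every man who declines. No choice of test, and no imputation based on this study's data, supplies a variable that is absent from one whole comparison group.

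At stake is how much the trial can say about who attends, stays and finds the programme acceptable. The plan intends to use that information in designing the next trial.

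**Working it through.** The plan states no power or precision for these explorations, so there is no figure of its own to reproduce.

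**Inputs from the documents**
- n = 30 (11.1).
- Two-sided alpha = 0.05 (11.2.1).
- Attendance at the 70% criterion: 0.70 × 30 = 21 attend all sessions, 9 do not.
- Retention at the 85% criterion: 0.85 × 30 = 25.5, so at least 26 retained and at most 4 not.

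**Assumptions not in the documents**
- Normally distributed scores with no ties at the median.
- A median split (15 above, 15 below).
- True differences between groups of 0.5 to 1.2 SD.

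**Step 1: what a median split can show for retention.** The most extreme table has all 4 non-retained men in one half. The two-sided Fisher p is then

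2 × C(15,4) / C(30,4) = 2 × 1,365 / 27,405 = 0.0996.

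This exceeds 0.05. With 3 men not retained the minimum rises to 2 × 455 / 4,060 = 0.224. So whenever at least 26 of 30 are retained, a 15/15 split cannot reach significance, however strong the association.

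**Step 2: dependence on the cut.** With a 10/20 split and 26 versus 4, all 4 non-retained men in the group of 10 gives C(10,4) / C(30,4) = 210 / 27,405 = 0.008. The same data could therefore be significant or not according to a cut that the plan leaves open.

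**Step 3: what a median split can show for attendance.** With 9 non-attenders the minimum p is 2 × C(15,9) / C(30,9) = 2 × 5,005 / 14,307,150 = 0.0007, so significance is possible. The test rejects only if at most 1 of the 9, or at least 8, lie above the median. Its actual type I error is

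2 × [C(15,9) + 15 × C(15,8)] / C(30,9) = 2 × (5,005 + 96,525) / 14,307,150 = 1.4%.

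**Step 4: simulated power for attendance** (20,000 runs per row, 21 versus 9)

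| Difference (SD) | Median split + Fisher | Mann-Whitney | t-test |
|---|---|---|---|
| 0.5 | 7% | 20% | 23% |
| 0.8 | 18% | 45% | 49% |
| 1.0 | 30% | 63% | 68% |
| 1.2 | 44% | 79% | 83% |

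For retention (26 versus 4), the median split with Fisher's test has 0% power throughout, as Step 1 requires. Mann-Whitney has 13%, 26%, 38% and 51% for the same four differences.

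**Step 5: which comparisons have data**

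| Outcome | Psychosocial scores available? |
|---|---|
| Attendance, retention | Yes, from the intake questionnaire |
| Exit acceptability measure | Yes, for men who complete the exit questionnaire |
| Agree versus decline | No: none for men who decline |

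The intake demographic and disease forms are likewise missing for men who decline. What exists for them is the eligibility screener, recorded in REDCap before consent (5.2).

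**The case against.** The strongest reply is that 11.2.1 already gives the right rule for continuous variables, that 11.2.2 never says that scores will be cut, and that the analyses are exploratory. On this view 11.2.2 merely lacks a cross-reference. Much of this stands. A reader might infer that the plan has no suitable method for numeric factors, but 11.2.1 names one; the fault is that the more specific section names a different test for every class of factor. A reader might also infer that Fisher's test is wrong throughout. It is not: attendance and retention are yes/no for each man, and factors such as race, employment status, nativity and relationship status are naturally categorical.

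A second reply concerns the power figures. They depend on an assumed median split and normal scores. The comparison is also not at equal type I error (1.4% against a nominal 5%), so a substantial part of the gap is the conservatism of Fisher's test on a small table and not information lost by cutting. That is fair, although an analyst following 11.2.2 would bear both costs. Even Mann-Whitney has only 45% power at 0.8 SD, so neither approach is confirmatory with 30 men.

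A third reply is that men who decline are not without data. That is correct. It would go too far to infer that agreeing and declining men cannot be compared at all, since eligible men have screener responses in REDCap. But the documents neither show the screener items nor say that they will be kept for this use. Section 12.0.4 commits to destroying or de-identifying collected information at the earliest opportunity, and items that are eligibility criteria will vary little among eligible men.

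Finally, the documents call only the outcome scales continuous totals (11.2.3). That the psychosocial scales also give numeric scores is an inference, though a safe one for multi-item scales.

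**Conclusion.** The point holds in a limited form. Section 11.2.2 conflicts with 11.2.1 for numeric factors and, taken literally, requires cut points that the plan does not state. One comparison within its wording, agree versus decline by psychosocial factors, has no data for men who decline.

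Under the median-split assumption the loss is sizeable: for attendance, Fisher's test has between about one third and just over one half of the power of Mann-Whitney (7/20 = 35% at 0.5 SD, 44/79 = 56% at 1.2 SD), and for retention it cannot reach significance once the 85% criterion is met. Other cuts would give other figures.

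A reader might infer that the feasibility conclusion itself is at risk. The documents do not support that: the 70% and 85% criteria are simple proportions, and neither they nor the pre-post analyses depend on these tests. Because the affected analyses are exploratory, the severity is minor.

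**What to change.** Revise the sentence in 11.2.2 as follows:

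1. Keep Fisher's exact test for categorical factors.
2. For numeric factors, refer to the 11.2.1 tests (Mann-Whitney or t-test) on the uncut score, and report effect estimates with 95% confidence intervals. If the exit acceptability measure is itself analysed as a score, the correlation coefficients already named in 11.2.1 cover its relation to numeric factors.
3. Restrict psychosocial comparisons to attendance, retention and, where outcome data exist, the exit acceptability measure.
4. Limit any agree-versus-decline comparison to named pre-consent screener items that vary among eligible men, on condition that keeping and using them is permitted. Otherwise report only the proportion who agree.

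Items 1 to 3 cost a few lines of text and need no new data. Item 4 is not certain to be free: the team must first confirm which screener items are held, and whether the consent and privacy arrangements allow their analysis for men who decline.
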